10.6. Planned Methods of Analysis

All eCRF data, lab data transfers, and any outcomes derived from the data will be provided in the patient listings. Patient data listings will be presented for all patients enrolled into the study. Descriptive summary statistics including n, mean, median, SD, standard error, interquartile range (25th percentile, 75th percentile), and range (minimum, maximum) for continuous variables, and counts and percentages for categorical variables will be used to summarize most data. Where appropriate, p-values will be reported. All statistical tests will be conducted using 2-sided tests with 5% Type I error rate unless otherwise stated.

All primary and secondary endpoints will be assessed on ITT and PP Populations, with the former being the basis for the primary efficacy analysis. Placebo patients from Cohort A and Cohort B will be pooled for analysis. All safety assessments will be performed on the Safety Population.

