4.5. Analysis Sets

Screened patients will be defined as those patients who signed informed consent/assent forms.

The Safety Set will include all randomized patients who received at least 1 dose of Study Drug (ISIS 721744 or placebo). Analyses or summaries on the Safety Set will be performed by actual treatment group.

The Full Analysis Set (FAS) will include all randomized patients who received at least 1 dose of Study Drug (ISIS 721744 or placebo). Analyses or summaries on FAS will be performed by randomized treatment group.

The Per-Protocol Set (PPS) will include all patients in the FAS who are treated according to the protocol without any major deviations that could compromise the interpretation of efficacy. Other major deviations that could compromise the interpretation of efficacy will be determined prior to unblinding for statistical analyses. Analyses or summaries on the PPS will be performed by randomized treatment group.

The PK Population will include all patients who are randomized and received at least 1 dose of Study Drug of ISIS 721744 and have at least 1 evaluable PK sample.

The FAS is the basis for the primary efficacy analysis. All efficacy and pharmacodynamics (PD) endpoints will be assessed based on the FAS. Efficacy endpoints may be analyzed based on the PPSs which is specified in the Section 4.9.

All safety assessments analyses or summaries will be performed on the Safety Population.

The number of patients in each analysis population will be summarized by treatment group (ISIS 721744 80 mg every 4 weeks, ISIS 721744 80 mg every 8 weeks or pooled placebo) and overall for all randomized patients. A summary of reasons for patients to have been excluded from the PPS will be provided. A by-patient listing for analysis populations and reason for exclusion will be provided.

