4.9. Efficacy Evaluation

The FAS is the basis for the primary efficacy analysis and the main efficacy analyses for all other efficacy endpoints. Analyses based on the PPS, if applicable, are described for each endpoint within this section. By-patient listings will be provided.

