4.9.1.4. Multiple Comparisons/Multiplicity

The multiplicity will be controlled by using a hierarchical ranking strategy in the following testing sequence. Should the null hypothesis for the primary efficacy endpoint be rejected, other endpoints will be tested in order. If any test is not statistically significant, the test(s) at the lower rank will be considered exploratory. Other statistical analyses planed in this SAP but not listed below are considered as exploratory analyses. No adjustment will be made. All tests will be conducted at a two-sided alpha level of 0.05.

- 1. Primary efficacy endpoint analysis: Comparison of the time-normalized number of Investigator-confirmed HAE attacks (per every-4-week) from Week 1 to Week 25 between ISIS 721744 80 mg every 4 weeks group and pooled placebo group
- 2. Comparison of the time-normalized number of Investigator-confirmed HAE attacks (per every-4-week) from Week 5 to Week 25 between ISIS 721744 80 mg every-4-weeks group and pooled-placebo group
- 3. Comparison of the number of patients with a ≥ 70% reduction from baseline in Investigator-confirmed HAE attacks (per every-4-week) from Week 5 and Week 25 between ISIS 721744 80 mg every-4-weeks group and pooled-placebo group
- 4. Comparison of the percentage of Investigator-confirmed HAE attack-free patients from Week 5 to Week 25 between ISIS 721744 80 mg every-4-weeks group and pooled-placebo group
- 5. Comparison of the time-normalized number of moderate or severe Investigator-confirmed HAE attacks (per every-4-week) from Week 5 to Week 25 between ISIS 721744 80 mg every-4-weeks group and pooled-placebo group
- 6. Comparison of the number of Investigator-confirmed HAE attacks requiring acute therapy (per every-4-week) from Week 5 to Week 25 between ISIS 721744 80 mg every-4-weeks group and pooled-placebo group
- 7. Comparison of the change in AE-QoL total score at Week 25 between ISIS 721744 80 mg every-4-weeks group and pooled-placebo group
- 8. Comparison of the time-normalized number of Investigator-confirmed HAE attacks (per every-4-week) from Week 1 to Week 25 between ISIS 721744 80 mg every-8-weeks group and pooled-placebo group
- 9. Comparison of the time-normalized number of Investigator-confirmed HAE attacks (per every-4-week) from Week 5 to Week 25 between ISIS 721744 80 mg every-8-weeks group and pooled-placebo group

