- 23. Comparison of the percent of patients who are well controlled on the AECT at Week 25 between ISIS 721744 80 mg every-4-weeks group and pooled-placebo group
- 24. Comparison of the percent of patients who are well controlled on the AECT at Week 25 between ISIS 721744 80 mg every-8-weeks group and pooled-placebo group

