TP-GDO-WW-016-08 CONFIDENTIAL Project Document Version No. 2.0 Effective Date: 26 Nov 19 Project Document Effective Date: 13 Dec 2023 Related to: SOP-GDO-WW-019 Page 35 of 61

1. How often have you had angioedema?	Very often = 0, Often = 1, Sometimes = 2, Seldom = 3, Not at all =4
2. QOL been affected by angioedema?	Very much = 0, Much = 1, Somewhat = 2, A little = 3, Not at all =4
3. Unpredictability of angioedema?	Very much = 0, Much = 1, Somewhat = 2, A little = 3, Not at all =4
4. Angioedema been controlled?	Not at all = 0, A little = 1, Somewhat = 2, Well = 3, Very well =4

The AECT total score is the summation of scores of 4 questions and can be used to identify patients with poorly controlled disease by working with a cutoff value of greater than or equal to 10 points. Patients with the total score less than 10 points (0–9) in the AECT have poorly controlled disease whereas patients with controlled disease score 10–16 points. The AECT will be completed by the patient.

The number and percentage of patients who are well-controlled on the AECT at Week 25 will be summarized by treatment group.

The clinical response of well controlled patients on AECT at Week 25 will be analyzed on all patients with at least one non-missing AECT value at a post-baseline visit, using the same method as described for clinical responses in Section 4.9.3.3. However, the baseline and treatment-by-baseline interaction is not included for AECT (i.e., no covariates in the logistic regression).

For patients who discontinued the Treatment Period early and started OLE, and patients who discontinued the Treatment Period early and were lost to follow-up before Week 25, before calculating the responder of well controlled on the AECT at Week 25, missing AECT total score will be imputed by LOCF which is described in Section 4.9.1.3.

Sensitivity Analyses

To evaluate the robustness of inferences made on the imputed data using LOCF, a sensitivity analysis on all patients with at least one non-missing AECT value at a post-baseline visit will be performed based on imputed data by using MI methods assuming J2R which is described in Section 4.9.1.3. For each imputed data set, the responder will be derived, and main analysis described above will be performed. Results will be combined using Rubin's rules.

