A sensitivity analysis on all patients with at least one non-missing AECT value at a post-baseline visit based on imputed data by using LOCF in Section 4.9.1.3 will also be performed. In the sensitivity analysis, the logistic regression will include the baseline AECT total score (continuous) as a covariate. Missing baselines will be imputed first by the average of available baselines across all patients in the FAS.

4.9.3.7. Change from Baseline in Angioedema Quality of Life (AE-QoL) Questionnaire Total Score at Week 25.

Quality of life will be assessed by the AE-QoL questionnaire during Screening, Treatment, and Post-Treatment Periods as outlined in Protocol Appendix A.

TP-GDO-WW-016-08 CONFIDENTIAL Project Document Version No. 2.0 Effective Date: 26 Nov 19 Project Document Effective Date: 13 Dec 2023 Related to: SOP-GDO-WW-019 Page 36 of 61

The AE-QoL questionnaire is a validated tool to assess symptom specific health-related quality of life impairment in patients suffering from recurrent angioedema (Weller *et al.* 2012). The AEQoL is a self-administered questionnaire that can be completed in less than 5 minutes; it comprises 17 questions across 4 domains: functioning, fatigue/mood, fears/shame, and food. Each domain includes the following questions:

Functioning	How often have been restricted in the area of Q1. Work; Q2. Physical activity; Q3. Leisure time; Q4. Social relations
Fatigue/mood	Q6. Difficulty falling asleep; Q7. Wake up during the night; Q8. Tired since not sleeping well; Q9. Trouble on concentrating; Q10. Depressed
Fears/shame	Q12. Swelling episode burden you; Q13. Afraid swelling could occur suddenly; Q14. Afraid frequency of the swelling increase; Q15. Ashamed to go out in public because of swelling; Q16. Embarrassed or self-conscious because of swelling; Q17. Afraid treatment has negative long-term effects
Food	Q5. Restrict eating and drinking; Q11. Limit your choices of food/beverage

The AE-QoL can be used to calculate scores for the 4 individual domains and can also be used to determine a total score. The AE-QoL will be completed by the patient.

AE-QoL will be evaluated by determining its four individual domain scores and a total score. Each item answered by the patient scores between 0 and 4 points depending on the answer option chosen by the patient: Never = 0, Rarely = 1, Occasionally = 2, Often = 3, Very often = 4. The AE-QoL domain scores and total score are calculated by using the following formula:

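### No planned AECT test runs on the full FAS: the main analysis and both sensitivity analyses leave out treated patients with no post-baseline AECT, contrary to the SAP's general rule and without a recorded exception

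*Combined protocol and SAP*

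**What the plan says.** **General rule.** SAP 4.5 defines the FAS by randomisation and at least one dose, with no post-baseline requirement. It then states: "All efficacy and pharmacodynamics (PD) endpoints will be assessed based on the FAS". SAP 4.9 repeats this: "The FAS is the basis for the primary efficacy analysis and the main efficacy analyses for all other efficacy endpoints". Protocol 10.6 has the equivalent rule under its own set names: "All primary and secondary endpoints will be assessed on ITT and PP Populations".

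**AECT rule.** In SAP 4.9.3.6 the main analysis is a logistic regression without covariates, with last observation carried forward (LOCF). It "will be analyzed on all patients with at least one non-missing AECT value at a post-baseline visit". The multiple-imputation analysis under jump-to-reference (J2R) uses the same set. So does the baseline-adjusted one: "A sensitivity analysis on all patients with at least one non-missing AECT value at a post-baseline visit based on imputed data by using LOCF".

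**Status of the test.** SAP 4.9.1.4 includes "Comparison of the percent of patients who are well controlled on the AECT at Week 25" at rank 23 (every 4 weeks) and rank 24 (every 8 weeks), the last two of 24. The section adds: "All tests will be conducted at a two-sided alpha level of 0.05".

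**Recorded changes.** SAP 4.16 explains the move from ITT to FAS. The revision history mentions the AECT change to LOCF. Neither mentions a restricted AECT population.

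**The concern.** The AECT set is defined by something that happens after randomisation, namely whether a questionnaire was ever completed on treatment. It is not one of the analysis sets in SAP 4.5. Loss of this kind can differ between arms. SAP 4.9.3 also commits each secondary endpoint to a treatment-policy comparison, which is meant to keep treated patients in whatever happens later.

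Sensitivity analyses would normally show whether such an exclusion matters. Here they change the imputation method (J2R) or the covariates (baseline AECT) but never the set of patients. A reader of the results could not tell from any planned AECT test whether the exclusion moved the answer. With about 20 patients in each of two arms, a single patient is a visible share of the denominator.

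**Working it through.** **1. Arm sizes.** The plan gives 84 patients, cohorts 2:1, and active to placebo 3:1 within each cohort (SAP 3.1, 4.15).
- Every 4 weeks: 84 × 2/3 × 3/4 = 42.
- Every 8 weeks: 84 × 1/3 × 3/4 = 21.
- Pooled placebo: 84 × 2/3 × 1/4 + 84 × 1/3 × 1/4 = 14 + 7 = 21.

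This reproduces the stated 42/21/21. The lay summary at the front of the combined document reports 45, 23 and 22 participants. I use those as the FAS sizes.

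**2. Share of one patient.** 1/45 = 2.2, 1/23 = 4.3 and 1/22 = 4.5 percentage points.

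**3. Test.** With no covariates, logistic regression reduces to a 2×2 table. With x1 of n1 well controlled on active and x0 of n0 on placebo:
- log OR = ln[ x1(n0 − x0) / ((n1 − x1) x0) ]
- SE = √[1/x1 + 1/(n1 − x1) + 1/x0 + 1/(n0 − x0)]
- two-sided Wald p from z = log OR / SE

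The documents give no AECT response rates and no count of patients without a post-baseline AECT. The tables below are assumptions, chosen near p = 0.05 to show what one or two patients can do.

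**4. Every 8 weeks, one active patient without a post-baseline AECT.**
- Restricted set, 14/22 v 7/22: OR = 3.75, log OR = 1.322, SE = 0.637, z = 2.07, p = 0.038.
- FAS, patient counted as not well controlled, 14/23 v 7/22: OR = 3.33, log OR = 1.204, SE = 0.626, z = 1.92, p = 0.055.
- FAS, patient in truth well controlled, 15/23 v 7/22: OR = 4.02, p = 0.028. The conclusion does not change.

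**5. Same arm sizes, but placebo loses the patient.**
- Restricted set, 14/23 v 7/21: p = 0.072.
- FAS, patient counted as not well controlled, 14/23 v 7/22: p = 0.055.

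Here the restriction works against the drug, so the direction is not fixed.

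**6. Every 4 weeks, against placebo 7/22.**
- One patient: 26/44, p = 0.040, becomes 26/45, p = 0.0497. Still below 0.05.
- Two patients: 25/43, p = 0.048, becomes 25/45, p = 0.072.

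**7. Is the restriction forced by the method?** SAP 4.9.1.3 lets LOCF carry post-baseline values only, so a patient with none receives no value. That explains the two LOCF analyses. It does not explain the J2R analysis: its imputation model in 4.9.1.3 includes the baseline score, and a missing baseline is first filled with the FAS average. Every FAS patient can therefore be imputed. SAP 4.9.3.7 runs the parallel J2R analysis of AE-QoL on the FAS.

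**8. Who can be affected?** The Week 5 AECT window is Days 2–43 (SAP 4.2.3), and early-termination and follow-up assessments are mapped to analysis visits. AECT is also due at the treatment early-termination visit (Protocol Appendix A), planned 28 days after the last dose (Protocol 8.8.1). A patient must miss all of these occasions to be excluded.

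**The case against.** The case for leaving the plan alone has four parts.

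- **The set follows from LOCF and is stated openly.** This stands for the two LOCF analyses. Nor does an FAS label by itself solve the problem: the AE-QoL main model is on the FAS without imputing post-baseline scores, so a patient with none contributes no outcome there either. The argument does not cover the J2R analysis or the missing entry in SAP 4.16.
- **Few or no patients qualify.** This stands. The visit schedule makes such patients rare, and the documents show none.
- **The tests come last.** This stands. Rank 23 is confirmatory only if all 22 earlier tests succeed, rank 24 also needs rank 23, and nothing follows them.
- **The protocol conflict is largely disclosed.** This stands for ITT to FAS, which SAP 4.16 explains. Only the AECT subset is unrecorded.

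Two stronger readings are tempting. A reader might infer that a patient who leaves before any AECT is a treatment failure. The documents do not support that: under treatment policy the Week 25 status of an unmeasured patient is unknown, and the listed reasons for stopping include COVID-19 and war. Counting all such patients as failures is a composite choice. The SAP's own AE-QoL responder rule does so only for stops due to adverse events or lack of efficacy, and excludes the rest. A reader might also infer that the restriction flatters the drug. Step 5 shows the reverse when placebo loses the patient.

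**Conclusion.** The point holds as an internal inconsistency and a gap in the sensitivity analyses. AECT is tested on an unlisted subset, against the rule in SAP 4.5 and 4.9, and no planned AECT test examines the exclusion. The descriptive AECT count and percentage names no restricted set, but it is not a test.

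The likely size is small. The number affected is unknown and may be zero, in which case nothing changes. If it is one or two, a borderline p-value can cross 0.05 in either arm, but only in tables selected for being borderline and under an assumed outcome for the missing patients. The documents do not show that the AECT result is biased, in which direction, or that any other ranked test is touched.

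**What to change.** 1. Run the J2R multiple-imputation analysis on the full FAS, imputing patients with no post-baseline AECT from the Day 1 score.
2. Add a FAS sensitivity analysis that counts these patients as not well controlled, and label it a conservative convention rather than the treatment-policy estimate.
3. Report the number excluded in each arm.
4. Either move the main analysis to the FAS with a stated rule for these patients, or keep it and record the AECT exception in SAP 4.5 and 4.16.

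The cost is a wording change and a little more analysis work. Responder percentages may be slightly lower on the FAS.

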4.9.1.2. Adjustments for Covariates

The primary efficacy endpoint is time-normalized number Investigator-confirmed HAE attacks. Run-in period time-normalized attack rate as a baseline as well as the interaction of baseline and treatment will be included in the model as a covariate.

Baselines and the interaction of baseline and treatment may be a covariate in change from baseline analyses models for secondary endpoints, if applicable.

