 λ (ISIS 721744, tipping point) = λ (ISIS 721744, MAR-imputed) \times δ (ISIS 721744) λ (Placebo, tipping point) = λ (Placebo, MAR-imputed) \times δ (ISIS 721744)

The sequences of both λ starts at 1, where λ (ISIS 721744, tipping point) is increased by 0.25 upwards and λ (Placebo, tipping point) goes backwards to 0. The increment of 0.25 may be subject to adjust in case the tipping points are not yet to be discovered. The upper limit may expand further in case the 'tipping-point' that yields non-significant conclusion has not appeared yet. Under each combination of λ (ISIS 721744, tipping point) and λ (Placebo, tipping point), the same analysis method as Missing at Random (MAR) is applied to acquire the pvalue of the analysis. For example, if there are 6 numbers (from 1 to 2.25 by 0.25) set as δ, there should be in total 36 corresponding p-values in the whole tipping point analysis.

For each imputation method used, at least 100 imputed datasets will be generated.

Multiple Imputation Jump-to-Reference (J2R) – AECT Total Score and AE-QoL Total Score

The Markov Chain Monte Carlo (MCMC) method will be used under the multivariate normality assumption to impute the missing AE-QoL total score and AECT total score by treatment group. The variable list for imputations will include the baseline score, as well as all available post-baseline scores within the treatment period, in the order of protocol defined visits. The SAS procedure PROC MI will be used in the multiple simulation. EM algorithm will be used to derive a set of initial parameter estimates for MCMC method. A non-informative prior (Jeffreys' prior) will be used to derive the posterior distribution of the parameters. In case there are missing baselines, it will be imputed first by the average of available baselines across all patients in the FAS. In the case of non-monotone missing pattern, MCMC method will be used first so that each imputed data set has a monotone missing pattern based on the order of the variable list.

TP-GDO-WW-016-08 **Project Document Version No. 2.0 CONFIDENTIAL** Effective Date: 26 Nov 19 Related to: SOP-GDO-WW-019

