For each of the clinical response, the odds ratio, corresponding 95% confidence intervals and p-value will be provided by using a logistic regression model with the baseline, and the treatment-by-baseline interaction as covariates. Odds Ratio is showing the strength of the association between the treatment effect and the clinical response.

Odds Ratio =
$$(p_1/(1-p_1)) / (p_2/(1-p_2))$$

Where

p₁ = proportion of responder of ISIS 721744 80 mg every 4 weeks (or every 8 weeks)

 p_2 = proportion of responder of the pooled Placebo

Odds Ratio ranges from 0 to infinity. When Odds Ratio = 1, there is no association; when Odds Ratio > 1, patients in the active treatment group are more likely than patients in the placebo group to be responders.

The responder is derived based on time-adjusted Investigator-confirmed HAE attack rate per every-4-week. For patients who discontinued the Treatment Period early and started OLE, and patients who discontinued the Treatment Period early and were lost to follow-up before Week 25, the HAE attack rate per every-4-week for each treatment group is considered as the same before and after withdrawal.

Main analysis will be based on FAS.

Sensitivity Analysis

To evaluate the robustness of inferences made on the main analysis, a sensitivity analysis on FAS will be performed based on imputed data by using MI methods assuming J2R which is described in Section 4.9.1.3. For each imputed data set, the percentage reduction will be calculated and main analysis described above will be performed. Results will be combined using Rubin's rules.

4.9.3.4. Percentage of Investigator-Confirmed Hereditary Angioedema (HAE) Attack-Free Patients from Week 5 to Week 25

The clinical response of Investigator-confirmed HAE attack-free from Week 5 to Week 25 will be analyzed using the same method as described for clinical responses in Section 4.9.3.3.

For patients who discontinued the Treatment Period early and started OLE, and patients who discontinued the Treatment Period early and were lost to follow-up before Week 25, the HAE attack rate per every-4-week for each treatment group is considered as the same before and after withdrawal.

Main analysis will be based on FAS and PPS.

TP-GDO-WW-016-08 Effective Date: 26 Nov 19 Related to: SOP-GDO-WW-019 CONFIDENTIAL Project Document Version No. 2.0

Project Document Effective Date: 13 Dec 2023 Page 34 of 61

Sensitivity Analysis

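### The alpha-controlled AECT responder test ignores the Day 1 score; swapping it with the SAP's own baseline-adjusted sensitivity model is a cheap efficiency gain, not the repair of an error

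*Combined protocol and SAP*

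**What the plan says.** SAP 4.9.1.4 places the every-4-weeks and every-8-weeks AECT comparisons with pooled placebo at ranks 23 and 24, each at two-sided 0.05. SAP 4.9.3.6 takes the responder method from 4.9.3.3 and then removes the covariates: "the baseline and treatment-by-baseline interaction is not included for AECT (i.e., no covariates in the logistic regression". The analysis uses patients with at least one post-baseline AECT value, with missing Week 25 totals filled by LOCF.

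The baseline score is available. The Schedule of Procedures (protocol Appendix A) has the AECT at Week 1, and SAP 4.2.2 defines baseline AECT as the Study Day 1 score. The last sensitivity analysis in 4.9.3.6 keeps the population and the LOCF data and adds that score: "In the sensitivity analysis, the logistic regression will include the baseline AECT total score (continuous) as a covariate". It has a rule for gaps: "Missing baselines will be imputed first by the average of available baselines across all patients in the FAS". The J2R imputation in 4.9.1.3 also uses it: "The variable list for imputations will include the baseline score, as well as all available post-baseline scores within the treatment period".

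Other text bears on the choice:
- Protocol 10.6.3.2 plans an unadjusted chi-squared or Fisher test for categorical endpoints.
- SAP 4.16 replaces that with baseline-adjusted logistic regression where the SAP so specifies, on the ground that adjustment makes the test more powerful.
- SAP 4.9.1.2 is permissive: "Baselines and the interaction of baseline and treatment may be a covariate in change from baseline analyses models for secondary endpoints, if applicable".
- In SAP 4.9.3.4, "HAE attack-free from Week 5 to Week 25 will be analyzed using the same method as described for clinical responses", so the attack-free model includes baseline and its interaction with treatment.

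**The concern.** SAP 4.16 gives a general argument for adjusting responder analyses, and the other alpha-controlled responder endpoints (at least 70% reduction, attack-free) follow it. AECT control does not, and no reason is given. That it is a status rather than a change from baseline does not explain the difference, because attack-free is also a status and its main model adjusts.

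The comparisons are small, with planned sizes of 42 v 21 and 21 v 21. If the Day 1 score predicts control at Week 25, the treatment-only test gives up power that the plan could have at almost no cost. Both models will be reported, but only the main one supplies the p-value that counts at ranks 23 and 24, and a miss at rank 23 makes rank 24 exploratory. No earlier test is affected.

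**Working it through.** **The plan's own power figure.** The only one is for the primary endpoint: at least 90% with 54 patients at 2:1 (36 and 18), at 1.38 v 13.26 attacks per 6 months (SAP 4.15).
- log(1.38/13.26) = -2.263
- SE = sqrt(1/(36 × 1.38) + 1/(18 × 13.26)) = sqrt(0.02013 + 0.00419) = 0.156
- |z| = 14.5, so power is about 100%

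The stated bound is met. It says nothing about the AECT, for which no power is given.

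**Inputs for the AECT.** From the documents: 42, 21 and 21 patients (SAP 4.15), two-sided 0.05, treatment-only main model, and a main-effect baseline model in the sensitivity analysis. Assumed: control rates, the correlation between baseline and Week 25 latent scores, and a baseline total with mean 6 and SD 3 on the 0 to 16 scale.

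**Treatment-only power at 70% v 35%, normal approximation.** Power = Φ[(0.35 − 1.96 × SE0)/SE1], with SE0 pooled and SE1 unpooled.
- 42 v 21: pooled rate (29.4 + 7.35)/63 = 0.583; SE0 = 0.1318; SE1 = sqrt(0.21/42 + 0.2275/21) = 0.1258; Φ(0.729) = 76.7%
- 21 v 21: pooled rate 0.525; SE0 = 0.1541; SE1 = sqrt(0.21/21 + 0.2275/21) = 0.1443; Φ(0.332) = 63.0%

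**With and without baseline, simulated.** There were 6,000 trials per cell, with a Wald test of treatment and the same correlation in both arms. The simulation error of each power near 76% is sqrt(0.76 × 0.24/6000) = 0.55 points.

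| Correlation | 42 v 21: unadjusted → adjusted | 21 v 21: unadjusted → adjusted |
|---|---|---|
| 0 | 76.5 → 76.5 (0.0) | 61.9 → 62.0 (+0.1) |
| 0.3 | 76.2 → 78.3 (+2.1) | 61.4 → 63.5 (+2.1) |
| 0.5 | 75.2 → 81.8 (+6.6) | 62.3 → 68.6 (+6.3) |
| 0.7 | 76.2 → 88.6 (+12.4) | 63.3 → 77.7 (+14.4) |

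A separate run of 10,000 trials per cell over three 35-point contrasts (65 v 30, 70 v 35 and 75 v 40%) gave changes of -0.8 to +0.7 points at correlation 0, and gains of 1.0 to 3.1 at 0.3, 4.8 to 7.6 at 0.5 and 11.7 to 14.9 at 0.7.

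**Unequal correlations, 70% v 35%.** With 0.2 on active drug and 0.5 on placebo, the gain is 2.4 points (42 v 21) and 2.8 (21 v 21). With 0 and 0.5 it is 0.3 and 1.9. With 0.3 and 0.7 it is still 6 to 8.

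**Larger effects.** At 85% v 30%, the gain over correlations 0 to 0.7 is at most 0.4 points (42 v 21, where unadjusted power already exceeds 99%) and at most 2.5 points (21 v 21).

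**Type I error at 35% v 35%.** It is 4.1 to 4.8% unadjusted and 4.2 to 4.7% adjusted.

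**Meaning of the odds ratio.** SAP 4.9.3.3 builds it from group proportions, the active one being the "proportion of responder of ISIS 721744 80 mg every 4 weeks (or every 8 weeks". At 65% v 30% this is (0.65/0.35)/(0.30/0.70) = 4.33. The odds ratio conditional on baseline is 4.39, 4.75, 5.74 and 8.75 at correlations 0, 0.3, 0.5 and 0.7.

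**The case against.** The strongest reply is that nothing is broken. The protocol plans an unadjusted test, 4.16 adjusts only where the SAP says so, 4.9.1.2 says baselines may be covariates and speaks of change-from-baseline models, and 4.9.3.6 states the exception openly. All of that stands. A reader might infer that 4.9.3.6 contradicts 4.16, or that the treatment-only test is invalid. The documents support neither: the qualifier in 4.16 allows the exception, and type I error is controlled. What remains is an exception without a reason.

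The second reply concerns size, and much of it stands. The 35-point contrasts are invented. The effects in the documents are larger, though none is an AECT rate: 13.26 v 1.38 attacks in the sample-size section, Phase 2 attack-free rates of 92.3% v none, and 4 of 5 patients attack-free on every-8-weeks dosing. An effective drug may also weaken the link between Day 1 and Week 25 scores in the active arm. And the AECT is tested only after 22 significant results. The power figures are not conditional on that, and trials that get there will mostly have large effects, where the gain is small.

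The third reply is that adjustment has costs. The treatment-only model is the one that matches the odds ratio defined in 4.9.3.3, and it needs no imputed baselines. A main-effect model would still differ from the interaction models of the other responder endpoints. These are real but modest costs. The main-effect form is the one the SAP already uses in the AECT sensitivity model, the PGIS logistic model (4.13.5) and the AE-QoL J2R ANCOVA (4.9.3.7).

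**Conclusion.** The point holds as a suggestion to consider. The alpha-controlled AECT test leaves out a baseline score that is collected and already modelled on the same data. The cost is power only, and its size depends on quantities the documents do not give. At 70% v 35% it runs from about 0 points to about 6 or 7 for correlations up to 0.5 in both arms, and is about 0 to 3 if the drug largely removes the association in the active arm. A reader might take the 12 to 15 point gains at correlation 0.7 as the expected loss, but they need that correlation in both arms and a moderate effect, and the documents support neither. If the effect is as large as 85% v 30%, the gain nearly vanishes for 42 v 21 and is small for 21 v 21.

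The case for the change is that it is lopsided: no detectable loss of power if baseline is uninformative, and some gain if it is not. Confidence is medium, because all rates and correlations are assumed.

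**What to change.** In SAP 4.9.3.6, make the logistic model with treatment and continuous baseline AECT total score (main effect only, with its existing missing-baseline rule) the main analysis at ranks 23 and 24. Keep the treatment-only model as the sensitivity analysis. The J2R analysis should use the adjusted model, since the section already ties it to the main one: "For each imputed data set, the responder will be derived, and main analysis described above will be performed". State that the odds ratio is conditional on baseline, and still report unadjusted proportions by group. The test order stays as it is. If the sponsor prefers the present main model, one sentence giving the reason would do.

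The cost is small: two specified models swap roles and no new data are needed. There are three downsides:
- The reported odds ratio departs from the group-proportion definition in 4.9.3.3 and must be labelled.
- The main test relies on a mean-imputed baseline wherever the Day 1 AECT is missing.
- The Fisher fallback is needed slightly more often, for example in 4.8% v 3.3% of simulated trials at 21 v 21, 85% v 30% and correlation 0.7.
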